Due to the cognitive impairment of intubated patients under ventilatory assistance, the consent will be obtained from the patient legal authorized representative (LAR). The LAR is determined as an individual or judicial or other body authorized under applicable law to make decisions on behalf of another individual. The LAR may provide consent on behalf of a prospective subject to the subject's participation in research. The terms surrogate decision maker or surrogate consent are also sometimes used. The LAR may be a family member or caregiver who has the legal authority to grant consent on behalf of another who has been invited to participate in research. The LAR will give consent by agreeing with the procedures/ benefits/ risks and participation. All questions/doubts from the LAR about the study will be clarified. When the patient regain consciousness or ability to consent, he/she will be fully informed about the study, and the research staff will obtain their signature. In order to reconsent, the patient will need to be fully aware in time, space, and person. The signed consent form will be maintained in research records.

The subject and/or LAR will be informed if he/she can withdraw from the study at any time without loss of benefits. Consent forms will be signed and dated by the subject, LAR and by the Principal Investigator or Investigators. The original consent will be maintained per IRB policy. Any critical information will be sent for inclusion in the medical records, if it affects patient's well-being and any future treatment. A signed copy of the consent form will be provided to the patient and LAR. Informed consent will be obtained prior to performance of any study procedures. Specifically: 1. No minors will be consented. 2. Subjects' LAR are given as much time as needed to ask questions and read over the consent. They are will be given a copy of the consent and can return at a later date if they need to discuss it with family members, etc. There will be an attachment in section S for the waiver of consent the form was retrieved from Section J- Adult assent.

Sub-population: We will recruit patients undergoing surgery in need of post-surgical ICU admission at BSLMC. This population is at risk of ICUAW. Patients will be consented either before surgery, or by a LAR on the day of surgery as described above.

E3. Pregnant woman/fetus

Will pregnant women and/or fetuses (as described in 45 CFR 46 Subpart B) be enrolled in the research?

No

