E4. Neonates

Will neonates of uncertain viability or nonviable neonates (as described in 45 CFR 46 Subpart B) be enrolled in the research?

No

E5. Children

Will children be enrolled in the research?

No

Section F: Design/Procedure

F1. Design

Select one category that most adequately describes your research:

c) Pilot

Discuss the research design including but not limited to such issues as: probability of group assignment, potential for subject to be randomized to placebo group, use of control subjects, etc.

We will prospectively recruit 40 patients at risk of ICUAW. Sample size is convenient and designed to explore acceptability and feasibility of objective tools for measurement. Eligible participants will be screened at BSLMC. Those who satisfied the inclusion and exclusion criteria and signed the informed consent form will be randomly assigned with ratio of 1:1 into two groups. Consenting will be performed with a legal authorized representative (LAR) that is present. When the subject regains consciousness and is aware in time, space, and person, he/she will be re-consented. If the subject decline to continue participation in the study, the subject will be withdrawn. The informed consent will be obtained from all participants and their LAR.

Sub-population: Post-surgical patients that are admitted to the ICU will be consented either before surgery, or by a LAR on the day of surgery as described above.

The study will be double-blinded (clinicians and patients) in intervention (IG) and control (CG) group. Both cohorts will be followed-up and monitored at 3 days, and then weekly for a total period of 4 weeks or until hospital discharge, whichever comes first. • Intervention group (IG). The IG (n=20) will be undergoing E-Stim therapy with an active device during the hospitalization period until 4 weeks or discharge, whichever comes first. To deliver E-Stim, 2 electrodes will be placed in each proximal gastrocnemius and Achilles tendons. • Control Group (CG). The CG (n=20) will be undergoing E-Stim therapy with a placebo device (5-10% currents) as described in the IG.

Inclusion Criteria:

-Any patient older than 18 years old admitted to the ICU within two days. -Patient can be intubated with ventilatory assistance or not.

Exclusion Criteria:

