Statistical Design: Independent t-test, U-test, or Chi-square (depends on type of variables) will be used to compare between groups (IG, and CG for key baseline descriptors including demographics and relevant clinical characteristics). Those descriptors which showed statistical significant difference will be considered as covariates for adjusting the results in the following assessments. Appropriate mixed models (linear for continuous or Generalized Estimating Equations (GEEs) for non-continuous or non-parametric variables) will be used to test the intervention effect for each of the primary or secondary outcomes. Results will be adjusted by covariates as described above.

P-values of 0.05 or less will be considered statistically significant based on a two-sided test unless otherwise noted. All variables will be tabulated descriptively at each scheduled time point (baseline, follow up and discharge date). For each continuous variable, the analyses will include the mean, standard deviation, minimum and maximum. For each categorical variable, the summary will include frequencies and percentages. Each variable will be analyzed using all available data. Baseline variables will be summarized using descriptive statistics. We assume that a successful intervention is also helpful to maintain subjects muscle mass, reduce neuromyopathy signs and increase perfusion. The measured parameters (e.g. sEMG, US, strength, Kent imaging, DPN Check, etc.) should change substantially from baseline to the end of the intervention. For example, the EMG amplitude values should show increased voltages. Next, for all continuous variables, pre-treatment scores will be regressed on post-treatment scores to form residualized change scores (e.g. sEMG, US, strength, Kent imaging, DPN Check, etc.). Correlations will then be generated among these scores to determine whether changes in sEMG factors are related appropriately with increases in (clinically assessed) functional capacities and self-report measures of activities at 1 month post-hospital discharge. ANOVA test will be used to examine significant difference between patients with severe risk factors for prolonged ICU stage (e.g. age, BMI, cardiovascular morbidities). Moderator effects will also be examined for exploratory purposes.

Section H: Potential Risks/Discomforts

H1. Potential Risks/Discomforts

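### At 20 per arm, choosing covariates by baseline significance misses most moderate imbalances in intubation status, so the covariates should be fixed in advance

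*Combined protocol and SAP*

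**What the plan says.** Section F1 (Design) plans 40 patients, "randomly assigned with ratio of 1:1 into two groups". It gives the arm sizes directly: "The IG (n=20) will be undergoing E-Stim therapy with an active device" and "The CG (n=20) will be undergoing E-Stim therapy with a placebo device". It names no sequence method, blocking, stratification or minimisation, and no other section does.

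The case mix is wide. The inclusion criteria state "Patient can be intubated with ventilatory assistance or not", and Section E2 adds a surgical sub-population: "We will recruit patients undergoing surgery in need of post-surgical ICU admission at BSLMC". Neither proportion is given.

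Section G2 (Data Analysis) handles imbalance in two steps. First, "Independent t-test, U-test, or Chi-square (depends on type of variables) will be used to compare between groups" on demographics and relevant clinical characteristics. Then: "Those descriptors which showed statistical significant difference will be considered as covariates for adjusting the results in the following assessments". Significance is P of 0.05 or less, two-sided. The descriptors are not listed, and neither intubation nor surgical status is named as a covariate.

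**The concern.** A baseline test has little power at 20 per arm, so a non-significant difference does not show that the arms are alike. Whether adjustment is needed depends on the size of the gap and on how strongly the factor predicts outcome. The P-value measures neither.

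The plan itself gives reason to treat intubation as prognostic. The background section lists endotracheal tubes and mechanical ventilation among the triggers of post-intensive care syndrome, and attributes lower-limb weakness mainly to immobilisation or sedation. Follow-up also stops at discharge if that comes before 4 weeks, so severity can affect how many assessments a patient contributes.

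At stake is the reliability of the arm comparison in a convenience sample of 40, on which G2 tests every primary and secondary outcome at 0.05.

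**Working it through.** **Inputs from the plan.** N = 40, 1:1, so 40 × 1/2 = 20 per arm, which agrees with F1. Two-sided threshold 0.05; chi-square for categorical descriptors (G2). The sample size has no power calculation to reproduce.

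**Assumptions not in the plan.** 30-50% intubated; a gap of 20 points (4 patients of 20) counts as material; outcome difference g by intubation status of 0.5, 1 or 1.5 SD.

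**Step 1: what the rule flags.** With a and b intubated in the two arms and K = a + b, Pearson chi-square without correction is X² = 40(a − b)² / [K(40 − K)].

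| Split | K | Gap | X² | P | Flagged |
|---|---|---|---|---|---|
| 12 v 8 | 20 | 20 points | 640/400 = 1.60 | 0.206 | no |
| 13 v 7 | 20 | 30 points | 1440/400 = 3.60 | 0.058 | no |
| 14 v 6 | 20 | 40 points | 2560/400 = 6.40 | 0.011 | yes |
| 8 v 4 | 12 | 20 points | 640/336 = 1.90 | 0.168 | no |
| 9 v 3 | 12 | 30 points | 1440/336 = 4.29 | 0.038 | yes |

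The smallest flagged gap is 30 to 40 points, depending on K. Fisher's test or Yates' correction flags no more than this.

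**Step 2: how often such gaps arise, for a given K.** With arms fixed at 20, the number intubated in one arm is hypergeometric (40, K, 20). The difference a − b has the same parity as K, so for odd K a gap of at least 4 means at least 5.

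| K | P(gap ≥ 20 points) | P(gap ≥ 20 points and unflagged) | Share missed |
|---|---|---|---|
| 12 | 30.1% | 21.8% | 73% |
| 13 | 17.6% | 13.5% | 77% |
| 14 | 32.0% | 22.4% | 70% |
| 16 | 33.3% | 31.1% | 93% |
| 19 | 20.5% | 14.9% | 73% |
| 20 | 34.3% | 31.7% | 93% |

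Values for 40 − K are identical. Over K = 12 to 28 the first probability runs from 18% to 34%.

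**Step 3: averaging over the unknown K.** Treating each arm's count as binomial (20, p):

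| p | P(gap ≥ 20 points) | Share missed | Product: arises and unflagged |
|---|---|---|---|
| 0.30 | 22.6% | 76.4% | 17.3% |
| 0.40 | 25.8% | 81.3% | 21.0% |
| 0.50 | 26.8% | 84.1% | 22.6% |

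**Step 4: consequence.** The unadjusted difference moves by gap × g. For 20 points this is 0.2 × 0.5 = 0.1 SD, 0.2 × 1 = 0.2 SD and 0.2 × 1.5 = 0.3 SD.

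In a simulated linear model (12,000 runs per setting, g = 1 SD), the SD of the effect estimate was 0.35-0.36 unadjusted, 0.34-0.35 under the significance rule and 0.32-0.33 with pre-specified adjustment. Among trials with an unflagged gap of 20 points or more, type I error was 7% unadjusted and about 5-6% adjusted. At g = 1.5 SD it was 7-8.5% against about 5%.

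**Step 5: effect of stratifying.** In 20,000 simulated trials with permuted blocks of 4, stratifying by intubation cut the chance of a 20-point intubation gap from about 22-26% (blocks, no strata) to 0%. The chance of such a gap in surgical status stayed at 20-24%, which is why the fix also needs a model term for it.

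**The case against.** **Randomisation already protects the comparison.** On average it does. Simulated overall type I error was about 5% unadjusted and 3.7-5.0% under the significance rule. A reader might infer that the plan's effect estimate is biased; the documents and the arithmetic do not support that.

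**The rule does correct large gaps.** It does: 9 v 3 is flagged. A reader might infer that the rule never corrects an imbalance in intubation, which would be too strong. What it misses is moderate gaps and, when the split is near half, some 30-point ones.

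**Stratification may be planned and unwritten.** F1 answers an ethics-form prompt and excludes nothing. A reader might infer unstratified simple randomisation, under which exactly 20/20 arises in only 12.5% of trials and arm sizes differ by 6 or more in 43%. Those figures apply only if simple randomisation is used, and the plan states 20 per arm. The G2 covariate rule stands whatever the allocation method.

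**Baseline outcomes may absorb the imbalance.** Partly. Outcomes are measured at baseline, Section F2 compares perfusion with baseline, and G2 forms residualised change scores. But G2 does not commit the mixed models to adjust for the baseline outcome, and a baseline value does not capture a different rate of decline afterwards.

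**It is a pilot.** That limits the weight of the point, and the precision gain is modest. The plan nevertheless claims proof-of-concept effectiveness and tests outcomes at 0.05.

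**Conclusion.** The point holds for moderate imbalance. At 20 per arm the G2 rule misses 70-93% of intubation gaps of 20 points or more for the totals examined, or 76-84% averaged over the total. Such a gap arises and goes unflagged in about 17-23% of trials. It shifts the unadjusted difference by 0.1 SD (g = 0.5) to 0.3 SD (g = 1.5), before any absorption by baseline measures.

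These sizes rest on the assumed 30-50% intubated (50-70% is symmetric), the 20-point threshold and the assumed g. At g = 0.5 SD the harm is small. The harm is lost precision, conditional error in the realised trial and a covariate set chosen from the data.

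The factor must also vary: Aim 2 and Section J2 speak of intubated patients while the inclusion criteria admit both, and these sections must be reconciled.

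**What to change.** In G2, delete the significance-based covariate rule. State that every outcome model includes intubation at enrolment (yes/no) and post-surgical status (yes/no), whatever their baseline P-values. Baseline tables can stay as description.

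In F1, state that assignment uses permuted blocks of varying size, stratified by intubation at enrolment, so that the stated 20 per arm is approximately delivered. Surgical status is then handled by its model term.

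The cost is one or two degrees of freedom per model and one extra item at randomisation. REDCap, which the plan already names for data capture, is one place to hold the stratified list.

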- Less than 48 hours of ICU stay - Major foot problems such as active lower extremity wounds, major foot deformity (e.g., Charcot Foot), and/or previous major amputations - Demand-type cardiac pacemaker, implanted defibrillator, or other implanted electronic devices - Any conditions that may interfere with outcomes or increase the risk of the use of neuromodulation therapy based on the judgement of clinicians

F2. Procedure

Patients admitted to the ICU within 2 days will be eligible and enrolled in the study after obtaining consent form as previously indicated.

Then, we will perform baseline measurements that include:

(Primary outcomes) Myopathy test: gastrocnemius muscle endurance (surface electromyogram, Trigno Delsys) in response to 5 minutes of neuromodulation; and muscle thickness (gastrocnemius muscle ultrasound, Vscan Air).

(Secondary outcomes) Perfusion test: Plantar foot perfusion parameters (near infrared spectroscopy, Kent Imaging System). The Snapshot NIR camera is a non-invasive imaging device that visualizes and maps tissue oxygen saturation, oxyhemoglobin, and deoxyhemoglobin from the microvascular network of a particular area of the skin. The SnapShot NIR camera is classified as an oximeter, tissue saturation device. As indicated in the 510 (k) summary by Kent Imaging, the NIR SnapshotNIR is a class II device intended for use by healthcare professionals as a non-invasive tissue oxygenation measurement system that reports an approximate value of: - oxygen saturation (StO2), - relative oxyhemoglobin level (HbO2), and - relative deoxyhemoglobin (Hb) level. SnapshotNIR is based on multispectral imaging technology and performs spectral analysis at each point in a two-dimensional scanned area producing an image displaying information derived from the analysis. In the present study, this device has no diagnostic, decision making, nor treatment intent, it is an assessment camera for tissue perfusion status in real time. The camera is positioned 30-50 cm away from the desired skin area, and a picture is taken. The pictures will be collected from the plantar foot of the patients as in our previous protocols for electrical stimulation (H-47781, H-50753). The data collected will determine whether lower-extremity electrical stimulation improves perfusion to the distal foot by comparing each time point vs baseline and by group comparison (placebo vs active device).

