Neuropathy test: Sural nerve conduction/amplitude assessment (neuropathy, DPNCheck Device by Neurometrix Inc)

Biomarkers tests: Creatinine kinase, C-reactive protein, creatinine, potassium, myosin, serum lactate, arterial SpO2, duplex ultrasound for DVT will be collected from the electronic medical records. If biomarkers were not collected as a standard/regular procedure in the ICU; data will not be extracted from the electronic medical records. Research staff will not draw any blood samples.

Then, the patients will receive an individually programmed device to deliver neuromodulation to both gastrocnemius muscles simultaneously. The frequency of therapy will be 1 hour daily, and the duration will be up to 4 weeks or until hospital discharge, whichever comes first.

The coordinator will provide the ICU staff with a weekly spreadsheet showing utilization (therapy sessions/day) so compliance can be monitored. Also, the devices will monitor the time of usage to confirm hours of effective neuromodulation therapy to the skin.

Follow-up assessments will be performed at 3 days, and then weekly until 4 weeks or until hospital discharge, whichever comes first, by the research staff. The follow-up assessment will be identical to the baseline assessment.

In the final visit, we will assess muscle strength (ankle dynamometer, RoMech Digital Hanging Scale).

Additional measurements: - 1-month post-hospital discharge phone questionnaires: instrumental activity of daily living scale (IADL), community engagement (the Life Space Questionnaire), independence in daily living activities (KATZ), and anxiety (BAI).

Section G: Sample Size/Data Analysis

G1. Sample Size

How many subjects (or specimens, or charts) will be used in this study?

Local: 40 Worldwide: 40

Please indicate why you chose the sample size proposed:

Sample size is convenient and selected based on available resources to demonstrate feasibility and the proof of concept effectiveness of neuromodulation therapy for patients admitted to ICU and post-ICU. We plan to recruit 40 eligible subjects.

G2. Data Analysis

Provide a description of your plan for data analysis. State the types of comparisons you plan (e.g. comparison of means, comparison of proportions, regressions, analysis of variance). Which is the PRIMARY comparison/analysis? How will the analyses proposed relate to the primary purposes of your study?

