The risk to participants due to the optional assessments and surveys is considered minimal because all that is required is simple walking and balance movements in a controlled environment with an attendant present. This research routine will not place subjects at higher risk than normal activities of daily living, and no more risk of harm or discomfort is associated with these tests than the discomfort normally incurred while performing normal muscle stretching. Subjects will be allowed rest time between trials as needed.

Potential risk to the subject due to the pulse oximeter optional test is considered minimal; this device is non-invasive, non-toxic, and non-ionizing. The device will be placed on the subject's finger, and monitor their oxygen levels.

H2. Data and safety monitoring plan

Do the study activities impart greater than minimal risk to subjects?

No

H3. Coordination of information among sites for multi-site research

Is the BCM Principal Investigator acting as the SPONSOR-INVESTIGATOR for this multi-site research?

No or Not Applicable

Is BCM the COORDINATING CENTER for this multi-site research?

No or Not Applicable

Section I: Potential Benefits

Describe potential benefit(s) to be gained by the individual subject as a result of participating in the planned work.

There is potential benefit of prevention or improvement of hospital acquired weakness due to ICU stay, based on previous studies the neuromodulation therapy will improve blood flow, tissue perfusion and muscle activation. In addition, the participation in this study may help the investigators better understand the prevention of ICU-acquired weakness and post-ICU syndrome and may determine if this therapy has an impact in daily leaving and activities after getting discharged from the hospital.

Primary outcomes include myopathy (sEMG) and neuropathy (DPN Check) assessment. Secondary outcomes include perfusion (Kent Imaging), and biomarkers. This therapy will also help to determine if hospital length of stay, and time for extubating can be reduced (patient health record). The primary and secondary outcomes will be assessed at baseline, 3 days, and then weekly after completing 4 weeks or until hospital discharge, whichever comes first. Appropriate mixed models (linear for continuous or Generalized Estimating Equations (GEEs) for non-continuous or non-parametric variables) will be used to test the intervention effect for each of the primary or secondary outcomes.

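### The perfusion claim rests on a tissue-oxygenation camera, so recovery of arterial saturation alone can look like better foot perfusion in the comparison with baseline

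*Combined protocol and SAP*

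**What the plan says.** Aim 2, H1.2 (Section D) states that E-Stim will improve tissue perfusion, measured by near-infrared spectroscopy. Section F2 lists plantar foot perfusion as a secondary outcome and says of the camera:

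- It "visualizes and maps tissue oxygen saturation, oxyhemoglobin, and deoxyhemoglobin from the microvascular network of a particular area of the skin".
- It is "classified as an oximeter, tissue saturation device", and it "reports an approximate value of: - oxygen saturation (StO2), - relative oxyhemoglobin level (HbO2), and - relative deoxyhemoglobin (Hb) level".
- In this study "it is an assessment camera for tissue perfusion status in real time".
- "The data collected will determine whether lower-extremity electrical stimulation improves perfusion to the distal foot", and this will be judged "by comparing each time point vs baseline and by group comparison (placebo vs active device".

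G2 expects the Kent imaging values, among others, to change substantially between baseline and the end of the intervention. It tests the intervention effect on each outcome by mixed model or GEE. The only covariates it admits are baseline descriptors that differ significantly between arms.

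Arterial saturation appears in two places, neither tied to the camera image. Under biomarkers in F2, "arterial SpO2, duplex ultrasound for DVT will be collected from the electronic medical records", and only where routine care recorded it. H1 mentions an optional pulse oximeter test: "The device will be placed on the subject's finger, and monitor their oxygen levels". That test is not described in F2 or G2, and no pulse oximeter is among the five devices in Section P.

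**The concern.** The outcome is named for blood flow, but the instrument reports haemoglobin oxygenation. Tissue saturation depends on flow, on local oxygen use and on the saturation of the arriving arterial blood. That is general physiology; the documents neither state it nor give its size.

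F1 admits patients with or without ventilatory assistance and follows them through recovery for up to 4 weeks. Arterial saturation may well change between visits for reasons unrelated to the leg. If it improves, StO2 can rise at an unchanged flow. The rise is real, but calling it perfusion is not justified.

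The exposure is greatest in the comparison with baseline, which F2 names as evidence and where randomisation gives no protection. Without an SpO2 value tied to each image, nobody could later tell how much of a rise tracked arterial saturation.

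**Working it through.** The documents give no effect size, standard deviation or power for this outcome, and the sample of 40 is one of convenience. There is no planned figure to reproduce, so the check asks what happens when there is no perfusion effect at all.

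**Inputs from the documents.** 20 patients per arm, randomised 1:1 (F1); two-sided 0.05 (G2); two comparisons, with baseline and between arms (F2).

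**Assumptions, not in the documents.** Change in StO2 = b × change in SpO2 + noise. The slope b is 0.5 to 1.0 (1.0 means StO2 follows arterial saturation point for point at fixed extraction). Mean change in SpO2 is 0 to 4 points, with SD s of 2 to 3. The noise SD is 5 StO2 points. All 20 patients per arm are observed, and one time point is tested. Each setting was simulated 4,000 times, so the Monte Carlo standard error is at most √(0.25/4000) = 0.8 percentage points.

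**1. Change from baseline within one arm (one-sample t-test).** The expected StO2 change is b × (mean SpO2 change), with standard error √(b²s² + 5²)/√20. For b = 1, s = 2 and a 2-point rise, the standard error is √(4 + 25)/√20 = 5.39/4.47 = 1.20, so the mean sits 2/1.20 = 1.7 standard errors above zero with no change in flow. Share of trials with p < 0.05:

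| Mean SpO2 rise | b = 0.5, s = 2 | b = 0.5, s = 3 | b = 1, s = 2 | b = 1, s = 3 |
|---|---|---|---|---|
| 0 points | 4.9% | 5.5% | 4.9% | 5.2% |
| 2 points | 13.5% | 12.5% | 33.8% | 30.9% |
| 4 points | 40.1% | 36.5% | 89.0% | 83.2% |

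**2. Active versus placebo, SpO2 changing alike in both arms.** The unadjusted false-positive rate is 4.3% to 5.5% across all settings, and 4.5% to 5.8% with SpO2 change as a covariate. Adjustment shortens the standard error by about 1% to 13%.

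**3. Active versus placebo, SpO2 diverging between arms by D points after randomisation (s = 2).** The chance of a significant StO2 difference in that direction is Φ(bD/SE − 1.96), with SE = √(4b² + 25) × √(2/20).
- b = 1: SE = 5.39 × 0.316 = 1.70. D = 2 gives Φ(1.17 − 1.96) = 22%; D = 3 gives Φ(1.76 − 1.96) = 42%.
- b = 0.5: SE = 5.10 × 0.316 = 1.61. D = 2 gives Φ(0.62 − 1.96) = 9%; D = 3 gives Φ(0.93 − 1.96) = 15%.

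**4. Would SpO2 minus StO2 serve better as the outcome?** Its change carries (1 − b) × change in SpO2, where raw StO2 carries b × change in SpO2. At b = 0.5 these variances are equal, (1 − 0.5)² = 0.5², so nothing is gained. At b = 1 the SpO2 term vanishes, but two oximeter readings add 2m², with m the reading-error SD. This exceeds the s² removed once m > s/√2, which is 1.4 points at s = 2.

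**The case against.** The strongest reply is that the trial is randomised with a placebo device and blinded, and that G2's formal test is of the intervention effect. A reader might infer that unmeasured oxygenation biases that test. The documents do not support this. Recovery common to both arms cancels in expectation. A chance imbalance in SpO2 change (95% range ±1.96 × √(2/20) = ±0.62 SD) is ordinary sampling error already contained in the standard error. Step 2 bears this out, and this part of the objection stands in full. What remains for the arm comparison is some extra noise and any true divergence in oxygenation after randomisation. Section I raises the possibility that time to extubation could be shortened, so divergence cannot be ruled out, but nothing in the documents says it will occur.

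A reader might also infer that SpO2 minus StO2 should replace StO2 as the outcome. That goes too far. Follow-up SpO2 is measured after randomisation and might itself respond to treatment. The precision gain can be zero or negative (step 4), and the difference still mixes flow with oxygen use.

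Nor is SpO2 wholly unused. Section I makes biomarkers secondary outcomes, so a divergence in charted values could be seen. But those values depend on routine charting and have no link to the image time.

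Finally, this is a secondary outcome in a 40-patient pilot. That limits the weight of the point. It does not remove it, because F1 gives the feasibility of objective measurement tools as a purpose of the study.

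**Conclusion.** The point holds for what the outcome is called and for the comparison with baseline. F2 describes a tissue-oxygenation reading, draws a perfusion conclusion from it, and accepts change over time as evidence without tying SpO2 to the image. Under the stated assumptions and with no change in perfusion, a single within-arm test would be significant in 13% to 34% of trials after a 2-point rise in SpO2, and in 37% to 89% after a 4-point rise. It stays near 5% if mean SpO2 does not move. These figures are illustrative: the slope, the SDs and the size of the SpO2 rise are all assumed.

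The randomised comparison is sound against common shifts. Only a divergence in SpO2 between arms would mislead it: 9% to 22% at 2 points and 15% to 42% at 3 points, under the assumptions of step 3.

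**What to change.** In F2, record SpO2 at each near-infrared image, from a finger reading or, failing that, the charted value nearest in time.

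In F2 and G2:
- Describe the outcome as plantar tissue oxygenation, and align Aim 2 H1.2 with that wording.
- Keep StO2 as the analysed outcome and name it as such, since F2 lists three camera quantities without choosing one.
- Rest any E-Stim claim on the between-arm comparison, and present change from baseline as descriptive only.
- Report a sensitivity analysis using concurrent SpO2, either as a covariate or as the SpO2 minus StO2 difference, labelled as relying on a post-randomisation measurement.

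The cost is a few seconds per visit and some wording. The finger reading needs adding to the F2 procedures, because it now appears only as an optional test in H1. Oximeter error enters the sensitivity analysis, and the benefit there is small if SpO2 hardly varies. The sponsor also accepts a more modest conclusion, about tissue oxygenation and not blood flow.
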